## 15.2 Clinical Laboratory Evaluation

Laboratory parameters (serum chemistry, hematology, and urinalysis) will be collected at the following visits:

- Screening (Visit 1),
- Day 1 (Visit 3) and Day 14 (Visit 5) of Treatment Period 1,
- Day 1 (Visit 7) and Day 14 (Visit 9) of Treatment Period 2,
- End of Trial (Visit 10).

*Laboratory Tests:*

- **Hematology:** hemoglobin, hematocrit, mean corpuscular volume, mean corpuscular hemoglobin, mean corpuscular hemoglobin concentration, red blood cell count, white blood cell count with differential (neutrophils, lymphocytes, monocytes, eosinophils, and basophils), and platelet count.
- **Serum Chemistry / Biochemistry:** ALT, AST, alkaline phosphatase, gamma-glutamyl transferase, bilirubin (total, direct, and indirect), sodium, potassium, chloride, glucose, blood urea nitrogen, creatinine, albumin, amylase, uric acid, creatine kinase, calcium, magnesium, bicarbonate, lactate dehydrogenase, triglycerides, HDL cholesterol, and low-density lipoprotein cholesterol, and eGFR/1.73 m^2 CKD-EPI.
- **Urinalysis:** Albumin, creatinine, bilirubin, glucose, ketones, blood, nitrite, pH, protein, specific gravity, and microscopy (if indicated by macroscopic findings).

An evaluation will be done to compare the units for each laboratory test. Where units differ, the units will be converted to a standard unit, and the conversion factors will be provided in analysis data model (ADaM) specifications. The reference ranges can be found in the laboratory manual in Appendix 1 'Protocol Test Summary'. Laboratory values recorded as  $>x$  or  $<x$ , will be analysed as  $x$ .

Laboratory parameters will be summarized by treatment group using descriptive statistics at 'period baseline' and Day 14. Changes from 'period baseline' will also be summarized. For categorical urinalysis results, the number and percentage of subjects in each results category will be presented by treatment group. Here baseline is defined as the pre-dose value on the first day of administration for each period.

Additionally, laboratory parameters will be summarized overall, using descriptive statistics at study baseline and End of Trial, including change from baseline. Here, baseline is defined as the last non-missing measurement (scheduled, unscheduled, or repeat) collected before the first administration of study treatment in the study.

The categorization into low-normal-high (below lower reference range/ within reference range/ above upper reference range) of each result will also be summarized for each visit, presenting the number and percentage of subjects in each category.

Pregnancy (or follicle-stimulating hormone [FSH] levels), serology, and alcohol breath test results will not be summarized but provided in data listings.

A separate listing of any abnormal laboratory measurements recorded throughout the study will be provided.

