### 15.3 Vital Signs

Vital signs data will be collected on each study visit, including pre-dose and 2 hours ( $\pm 30$  minutes) post-morning dose on Day 1 and Day 14 of each treatment period. The following vital signs will be collected:

- Systolic blood pressure (mmHg)
- Diastolic blood pressure (mmHg)
- Respiration rate (beats/min)
- Pulse oximetry (%)
- Heart Rate (bpm)
- Temperature (C)

Vital signs will be summarized by treatment group using descriptive statistics at period baseline and at each post-baseline time point in the treatment periods. Changes from baseline will also be summarized. Here baseline is defined as the pre-dose value on the first day of administration for each period.

Additionally, vital signs will be summarized overall, using descriptive statistics at study baseline and End of Trial, including change from baseline. Here, baseline is defined as the last non-missing measurement (scheduled, unscheduled, or repeat) collected before the first administration of study treatment in the study.

Vital sign data will be listed for all subjects in the Safety population.

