#### 15.5 Electrocardiogram

Standard 12-lead ECGs will be performed at Screening, Day 1 and Day 14 of each treatment period, and End of Trial.

The following parameters will be collected:

- RR interval (sec)
- PR interval (msec)
- QRS (msec)
- QT (msec)
- QTcF (msec)

Descriptive statistics at baseline and at each post-baseline time point and changes from baseline will be summarized for each ECG parameter by treatment group. Baseline is defined as the pre-dose value on the first day of administration for each period.

ECG parameters will be summarized overall using descriptive statistics at study baseline and End of Trial, including change from baseline. Here, baseline is defined as the last non-missing measurement (scheduled, unscheduled, or repeat) collected before the first administration of study treatment in the study.

Overall interpretation results for ECGs will be summarized using shift tables (normal, abnormal not clinically significant [NCS], and abnormal clinically significant [CS]) comparing baseline to follow-up by treatment group. The percentages for the shift table will be calculated relative to the number of subjects that have both a baseline and follow-up assessment available at each visit.

ECG data will be listed for all subjects in the Safety population.

[figure not shown]

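### End of Trial lab and vital-sign changes are summarised only overall, pooling subjects about 14 and about 42 days off ADX-629 with no comparator

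*SAP*

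**What the plan says.** **Labs (SAP 15.2).** The by-treatment table covers two time points: "Laboratory parameters will be summarized by treatment group using descriptive statistics at 'period baseline' and Day 14". End of Trial is handled separately: "Additionally, laboratory parameters will be summarized overall, using descriptive statistics at study baseline and End of Trial, including change from baseline". The low/normal/high classification "will also be summarized for each visit, presenting the number and percentage of subjects in each category", with no grouping stated.

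**Vital signs (SAP 15.3).** The by-treatment summary is given at period baseline and "at each post-baseline time point in the treatment periods", which leaves End of Trial out. That visit again gets one pooled table: "Additionally, vital signs will be summarized overall, using descriptive statistics at study baseline and End of Trial, including change from baseline".

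**ECG (SAP 15.5).** There is a pooled table here too: "ECG parameters will be summarized overall using descriptive statistics at study baseline and End of Trial, including change from baseline". The section also plans by-treatment output that is not limited to the treatment periods: "Descriptive statistics at baseline and at each post-baseline time point and changes from baseline will be summarized for each ECG parameter by treatment group". Shift tables are planned "comparing baseline to follow-up by treatment group".

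**Protocol 10.5** asks for changes in labs, vital signs and ECG to be summarised by treatment and by time point. Protocol 5.2.2.7 collects all three at the End-of-Trial visit. SAP 16 states that nothing in the protocol's planned analyses has been changed.

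**The concern.** Safety and tolerability are the primary objective. The End of Trial visit is the scheduled safety check after the second treatment period, and in S2 it is the only scheduled post-treatment visit after ADX-629. At that visit the sequences have different histories. S2 has recently stopped ADX-629, whereas S1 stopped it weeks earlier and has since taken placebo.

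One pooled change from study baseline cannot separate a late drug effect from time trend, regression to the mean or placebo response. Sequence is the randomised grouping and would give a concurrent comparison at no cost in data, but the lab and vital-sign sections do not use it for this visit.

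The SAP is also uneven. Section 15.1.2 assigns each adverse event to the treatment received just before onset, so an event after Period 2 counts under ADX-629 in S2 and under placebo in S1. Lab and vital-sign values from the same interval lose that distinction.

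**Working it through.** **1. Timeline.** SAP 4 gives up to 3 weeks of screening, 2 weeks per treatment period, a 2-week washout and 2 weeks of follow-up. The sum is 3 + 2 + 2 + 2 + 2 = 11 weeks, which reproduces the SAP's stated duration.

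**2. Days since the last ADX-629 dose at End of Trial.** SAP 9 defines S1 as ADX-629 then placebo, and S2 as the reverse.

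- S2 = follow-up = 14 days.
- S1 = washout + placebo period + follow-up = 14 + 14 + 14 = 42 days.

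| Timing assumption | S2 | S1 |
|---|---|---|
| Nominal | 14 | 42 |
| Washout 14 ± 2 and dosing period 14 ± 2 (protocol 5.1, 7.1), follow-up 14 | 14 | 38 to 46 |
| Same windows, follow-up 1 to 2 weeks (SAP 4) | 7 to 14 | 31 to 46 |
| Visit on Day 29, last dose on Day 14 (SAP 9) | 15 | 43 |

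The gap between the sequences holds under every stated window.

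**3. Dilution in the pooled mean.** Let d be the effect in S2 at 14 days, r the ratio of the effect at 42 days to that at 14 days, and w the share of subjects in S2.

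Pooled effect / d = w + (1 − w) × r

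Neither w nor r is in the documents. The allocation ratio is not stated, so w = 0.5 is an assumption. For r, assume an effect half-life of h days, so that r = 2^(−28/h).

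| Assumed decay | r | Pooled / d at w = 0.5 |
|---|---|---|
| Gone by 42 days | 0 | 50% |
| h = 7 days | 0.0625 | 53% |
| h = 14 days | 0.25 | 62.5% |
| h = 28 days | 0.5 | 75% |
| h = 56 days | 0.71 | 85% |
| No decay | 1 | 100% |

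With r = 0 and w from 0.4 to 0.6, the ratio runs from 40% to 60%.

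**4. Is there an effect to dilute?** Protocol 3.2 gives mean plasma half-lives of 3.49 to 6.83 hours. Fourteen days is 336 hours, so 336 / 6.83 = 49 to 336 / 3.49 = 96 half-lives. An effect that follows plasma concentration would be absent in both sequences. The same section describes irreversible binding to RASP, so a longer effect is possible, but the documents do not show one in these safety measures.

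**5. What splitting by sequence shows.** S2 would show d and S1 would show r × d, a contrast of d × (1 − r). The pooled table shows no contrast for any r. With 50 subjects, assumed 1:1 allocation and no withdrawals, each column would hold 25.

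**6. ECG.** The by-treatment statistics and shift tables in SAP 15.5 could include End of Trial, since an ECG is recorded then. The SAP does not say whether that ECG belongs to the last treatment taken or to something else. Nor is the baseline settled: the by-treatment table uses each period's pre-dose value, and the pooled table uses study baseline.

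**The case against.** The strongest reply is that little depends on this table. It is an additional descriptive summary, and no test or decision rests on it. The by-treatment comparison at Day 14 is untouched. Adverse events after dosing are attributed to a treatment (SAP 15.1.2), and medically relevant lab or vital-sign abnormalities are recorded as adverse events (protocol 8.3.1.2). Listings are sorted by sequence or treatment (SAP Appendix A), so individual values can be recovered. The protocol also lets the SAP govern statistical language. All of this stands and keeps the point small. It does not supply a summary with a comparator, and a SAP that governs should still record the departure in section 16.

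A reader might draw three stronger conclusions, which the documents do not support:

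- *That a persistent drug effect is halved.* An effect that does not decay is present in both sequences and keeps its full size in the pooled mean. Halving needs 1:1 allocation, an effect still present at 14 days, and its disappearance by 42 days.
- *That all three domains are summarised only overall.* This is not established for ECG, where the problem is a missing assignment rule. It is also not established for the lab low/normal/high counts, whose grouping is unstated. The index of tables is not shown in the public copy, so the planned columns cannot be checked there.
- *That End of Trial is the only scheduled look after dosing.* Visit 7 takes labs, vital signs and ECG before the first Period 2 dose (protocol 5.2.2.4), about 14 days after Period 1 treatment. S1 is then about 14 days off ADX-629 and S2 has not yet received it, which is a cleaner contrast. The SAP uses these values as the Period 2 baseline, so a post-ADX-629 value in S1 serves as a placebo baseline.

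**Conclusion.** The point holds for labs and vital signs. Their End of Trial changes from study baseline are planned only as a pooled column that mixes about 14 with about 42 days off ADX-629. That column has no comparator and does not follow protocol 10.5, while SAP 16 reports no change. For ECG it is a request for clarification.

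Under an assumed 1:1 allocation the pooled mean shows 50% to 100% of the effect present in S2. The 50% figure is the worst case: present at two weeks and resolved by six. The missing comparator does not depend on the decay rate or the allocation.

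Two limits apply. The sequence contrast at End of Trial would not reveal an effect that does not decay, because S1 would carry it too. Withdrawals in Period 1 also blur the contrast: such S2 subjects never took ADX-629, and such S1 subjects may be seen about 14 days after it. Severity is low, because the main safety comparison and the attribution of adverse events are unaffected.

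**What to change.** - In SAP 15.2 and 15.3, and for the overall table in 15.5, present study baseline, End of Trial and change by sequence (S1, S2) as well as overall.
- In 15.2, state the grouping of the low/normal/high table at End of Trial.
- In 15.5, state which treatment an End of Trial ECG is assigned to in the by-treatment statistics and shift tables, and which baseline applies.
- Reconcile these sections with protocol 10.5, and list any remaining departure in SAP 16.
- Optionally, show the Visit 7 pre-dose values by sequence in the same layout.

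The cost is two extra columns in tables already planned, plus a few sentences of text. The S1/S2 notation is defined in SAP 9, and SAP 8 already presents baseline data by sequence with a total. No new data or modelling is needed.

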### 15.2.1 Low-density Lipoprotein Cholesterol

Low-density lipoprotein cholesterol (LDL-C) values will be summarized separately. The changes from baseline in LDL-C at Day 14 will also be analyzed using a similar approach as described for the key secondary efficacy endpoint, except that the values will not be log-transformed prior to analysis.

Additionally values at Day 14 will be categorized as follows, and the number and percentage of subjects in each category presented by treatment group:

- Normal: Less than 100 mg/dL
- Borderline: 100-129 mg/dL
- High: 130 mg/dL or more.

### 15.3 Vital Signs

Vital signs data will be collected on each study visit, including pre-dose and 2 hours ( $\pm 30$  minutes) post-morning dose on Day 1 and Day 14 of each treatment period. The following vital signs will be collected:

- Systolic blood pressure (mmHg)
- Diastolic blood pressure (mmHg)
- Respiration rate (beats/min)
- Pulse oximetry (%)
- Heart Rate (bpm)
- Temperature (C)

Vital signs will be summarized by treatment group using descriptive statistics at period baseline and at each post-baseline time point in the treatment periods. Changes from baseline will also be summarized. Here baseline is defined as the pre-dose value on the first day of administration for each period.

Additionally, vital signs will be summarized overall, using descriptive statistics at study baseline and End of Trial, including change from baseline. Here, baseline is defined as the last non-missing measurement (scheduled, unscheduled, or repeat) collected before the first administration of study treatment in the study.

Vital sign data will be listed for all subjects in the Safety population.

#### 15.4 Physical Examination

Physical examinations, including review of the major body systems, will be performed at various timepoints throughout the trial.

Major body systems include, but are not limited to the following:

- Ears/Nose/Throat
- Cardiovascular
- Respiratory
- Dermatological
- Musculoskeletal
- Gastrointestinal
- Endocrine/Metabolic
- Hepatic
- Lymphatic
- Immunological
- Neurological

Physical examination results will be included in data listings only.

#### 15.5 Electrocardiogram

Standard 12-lead ECGs will be performed at Screening, Day 1 and Day 14 of each treatment period, and End of Trial.

The following parameters will be collected:

- RR interval (sec)
- PR interval (msec)
- QRS (msec)
- QT (msec)
- QTcF (msec)

Descriptive statistics at baseline and at each post-baseline time point and changes from baseline will be summarized for each ECG parameter by treatment group. Baseline is defined as the pre-dose value on the first day of administration for each period.

ECG parameters will be summarized overall using descriptive statistics at study baseline and End of Trial, including change from baseline. Here, baseline is defined as the last non-missing measurement (scheduled, unscheduled, or repeat) collected before the first administration of study treatment in the study.

Overall interpretation results for ECGs will be summarized using shift tables (normal, abnormal not clinically significant [NCS], and abnormal clinically significant [CS]) comparing baseline to follow-up by treatment group. The percentages for the shift table will be calculated relative to the number of subjects that have both a baseline and follow-up assessment available at each visit.

ECG data will be listed for all subjects in the Safety population.

[figure not shown]

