# **Number of Subjects:**

Approximately 50 subjects are planned for enrollment.

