## 4.2 Endpoints

# 4.2.1 Primary Endpoints

The primary endpoints of this trial are:

- Incidence and severity of TEAEs and serious adverse events (SAEs)
- Observed values and changes from baseline of:
  - Laboratory safety parameters
  - Vital signs
  - 12-lead electrocardiogram (ECG) parameters

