#### 6.4 Exclusion Criteria

Subjects who fulfill any of the following criteria are not eligible for enrollment in the trial:

- 1. Current smoker (e.g., cigarettes, e-cigarettes, nicotine patches) including cannabis products; or previous smoker having given up smoking ≤12 months before screening, or has a history of smoking of >20 pack-years or the equivalent nicotine strength (see Section 7.9.3) at any time or has positive cotinine test result at screening.
- 2.
- 3. Active upper respiratory tract infection or recent significant change in pulmonary status that, in the opinion of the Investigator, could affect the conduct or outcome of the trial and that is documented by a physician within 4 weeks before the first dose of trial treatment.
- 4. Uncontrolled hypertension with systolic blood pressure ≥160 mmHg or diastolic blood pressure ≥90 mmHg at screening.
- 5. Prolonged QT interval corrected for heart rate using Fridericia's formula (QTcF) >440 ms or shortened QTcF <340 ms at screening, or history of significant tachycardia, bradycardia, acute or chronic cardiovascular disease or any clinically significant abnormalities in rhythm, conduction, or morphology of the resting ECG.
- 6. Elevated alanine aminotransferase (ALT), aspartate aminotransferase (AST), or bilirubin levels >2.0 × upper normal limits.
- 7. History or presence of gastrointestinal, hepatic disease, or any other condition known to interfere with absorption, distribution, metabolism, or excretion of drugs.
- 8. Acute or chronic renal disease or medical history of renal disease with estimated glomerular filtration rate (eGFR) ≤30 mL/min/1.73 m^2 calculated by Chronic Kidney Disease Epidemiology (CKD-EPI) equation or spot urine protein to creatinine ratio (sUPCR) >2000 mg/g (226 mg/mmol, as an estimate of approximate proteinuria >2 g/day) at screening.

CONFIDENTIAL Page 37 of 68

- 9. History of any malignancy within 5 years of screening except for basal cell or squamous cell in situ skin carcinomas or carcinoma in situ of the cervix that has been treated with no evidence of recurrence.
- 10. Taking disallowed concomitant medications (strong CYP1A2, CYP2B6, and CYP3A4 inhibitors) during the trial period (Section 7.9).
- 11. History of severe hypersensitivity or ongoing clinically significant hypersensitivity to ADX-629.

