## 4. STUDY DESIGN

ADX-629-CC-001 is a Phase 2, multicenter, randomized, double-blind, placebo-controlled, two-period crossover trial to evaluate the safety, tolerability, and efficacy of ADX-629 300 mg administered orally BID for 14 days to approximately 50 adult subjects with refractory or unexplained chronic cough.

Subjects will be screened over a period of up to 3 weeks. Eligible subjects will be randomized to one of two treatment sequences. Subjects in one sequence will receive ADX-629 in Treatment Period 1 and matching-placebo in Treatment Period 2, while subjects in the other sequence will receive the matching placebo in Treatment Period 1 and ADX-629 in Treatment Period 2.

[figure not shown]
Subjects will receive their allocated treatment for 2 weeks within each treatment period. Each subject will have a washout period of 2 weeks  $\pm$  2 days between the two trial periods and will undergo a follow-up assessment approximately 1 to 2 weeks after the last dose of trial treatment. Subjects will be required to attend visits for screening and at the start and end of each treatment period. Each visit will require the subject to attend the clinic or to be visited by research staff on consecutive days. At Screening (Visit 1) and on Days 0 (Visit 2 and Visit 6) and 13 (Visit 4 and Visit 8) of each treatment period, the subject will be fitted with a cough recorder to collect cough count data over a period of 24 hours. The cough recorder will be removed the next day once the 24-hour recording has been completed. The trial will include 5 cough recorder sessions in total.

The trial duration for each subject will be up to 11 weeks as follows: up to 3 weeks for screening, 2 weeks for each treatment period, a 2-week washout between treatment periods, and a 2-week follow-up period.

Should a subject discontinue trial treatment, they will be requested to participate in an early (ET) termination visit as soon as possible after the subject stops taking trial treatment. The subjects should have their follow-up visit 1 to 2 weeks after their last dose of trial treatment; however, if their ET visit is more than 1 week after their last dose, they will not be required to have a follow-up safety assessment.

The follow-up safety assessment will be conducted as an in-clinic visit for follow-up laboratory parameters, vital signs, or electrocardiogram (ECG) parameters.

The trial design is illustrated in Figure 1.

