## 8. GENERAL ANALYSIS CONSIDERATIONS

The statistical analyses will be reported using summary tables, listings, and figures (TLFs). The International Council for Harmonisation of Technical Requirements for Pharmaceuticals for Human Use (ICH) numbering convention will be used for all TLFs.

Unless otherwise noted, all statistical testing will be 2-sided and performed at the 0.05 significance level. Tests will be declared statistically significant if the calculated  $P$ -value is  $\leq 0.05$ .

Continuous variables will be summarized by presenting the number of observations, means, standard deviations (SDs), medians, minimums, and maximums.

Categorical variables will be summarized by presenting counts and percentages of subjects in corresponding categories. All possible categories defined in the CRF will be populated, even with zero counts. Percentages for missing values are omitted and do not account for the percent calculation of other categories. Percentages are based on the total category count, excluding the missing category if not otherwise mentioned. The total number of subjects is used as the denominator in certain tables (e.g., adverse events [AEs]). Footnotes will specify the percent basis in those cases.

Baseline summaries will be presented by treatment sequence and include a total summary column.

Individual subject data obtained from the eCRFs, external vendors, central clinical laboratory, central ECG laboratory, and any derived data will be presented by subject in data listings.

The version of the WHODrug and Medical Dictionary for Regulatory Activities (MedDRA) coding dictionaries used for coding of concomitant medications and medical histories, respectively, will be specified in the final Medical Coding Plan.

After all the data have been verified, coded if necessary, and entered into the database, a review will be performed.

The analyses described in this plan are considered a priori in that they have been defined before breaking the blind.

Any analyses performed after breaking the blind will be considered post hoc and exploratory. Post hoc analyses will be labeled as such on the output and identified in the CSR.

All analyses and tabulations will be performed using SAS® statistical software, version 9.4 or higher (SAS Institute Inc). Tables, listings, and figures will be presented in RTF format.

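### SAP 15.5 specifies no count, by treatment, of subjects whose QTcF is prolonged, although ECG parameters are a primary endpoint

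*SAP*

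**What the plan says.** Protocol 4.2.1 lists observed values and changes from baseline of "12-lead electrocardiogram (ECG) parameters" among the primary endpoints. SAP 3.3 repeats this.

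SAP 15.5 collects RR, PR, QRS, QT and QTcF and states: "Descriptive statistics at baseline and at each post-baseline time point and changes from baseline will be summarized for each ECG parameter by treatment group". For these summaries, baseline is the pre-dose value on the first day of each period. The content of the descriptive statistics comes from SAP 8: "Continuous variables will be summarized by presenting the number of observations, means, standard deviations (SDs), medians, minimums, and maximums".

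The one categorical ECG output is a shift table of the overall interpretation, "comparing baseline to follow-up by treatment group". Its percentages are based on the "number of subjects that have both a baseline and follow-up assessment available at each visit". Individual ECG values are listed for the Safety population.

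ECGs are scheduled at screening, on Day 1 and Day 14 of each period, and at End of Trial. Day 14 is therefore the only scheduled ECG after dosing starts within a period. SAP 8.3 adds early-withdrawal ECGs to Day 14 of the relevant period.

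The only QTcF limits in either document are for entry. Protocol 6.4, criterion 5, excludes subjects with "QTcF) >440 ms or shortened QTcF <340 ms at screening".

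**The concern.** A primary safety endpoint would normally be reported in a way that tells the reader how many subjects had a notable change on each treatment. For QTcF the plan gives averages, spread and extremes, but no such number.

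The SAP does categorise other variables: laboratory results as low, normal or high at each visit (15.2), LDL cholesterol in three bands (15.2.1) and compliance in five bands (14). QTcF, for which the protocol already names limits, has no category after entry.

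A prolongation confined to a few subjects would be diluted in the mean. The maximum shows one value per treatment, and the ADX-629 and placebo maxima may come from different subjects. Each subject is to receive both treatments, so the trial can show whether a subject with a long QTcF on ADX-629 also had one on placebo. No planned table uses that.

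**Working it through.** The plan states no QTcF sample size, power or precision, so there is no figure to reproduce. The check is of the text, followed by an illustration on assumed inputs.

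**Text check**

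1. Continuous outputs for QTcF by treatment (SAP 15.5 with SAP 8): n, mean, SD, median, minimum and maximum, for values and for changes. None is a count of subjects past a limit.
2. Categorical output: the shift in overall interpretation. The documents give no rule linking that interpretation to QTcF. As an example, a rise from 375 to 435 ms is 435 − 375 = +60 ms, yet 435 ms is still below the protocol's 440 ms entry limit, so the ECG could be called normal both times.
3. Listings hold every value but give no count.

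**Illustration**

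From the documents: "Approximately 50 subjects are planned for enrollment". Assumed, because the documents give no figures: 48 subjects evaluable on both treatments; SD of the QTcF change 10 to 14 ms; SD of the paired treatment difference 14 to 20 ms; and the sizes of the increases.

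1. Shift in the mean = (subjects affected × increase) / n.
   - 2 subjects at +60 ms: 2 × 60 / 48 = 2.5 ms.
   - 5 subjects at +40 ms: 5 × 40 / 48 = 4.17 ms.
   - Sensitivity to n for 2 subjects at +60 ms: 120 / 50 = 2.4 ms and 120 / 40 = 3.0 ms.
2. 95% half-width of a paired mean difference = 1.96 × SD / √48.
   - SD 14: 3.96 ms. SD 20: 5.66 ms.
   - The 2.5 ms shift lies inside both. The 4.17 ms shift lies inside the second but slightly exceeds the first.
   - The SAP plans no such interval. It is used here only to scale the shift.
3. The same subjects as counts: 2 / 48 = 4.2% and 5 / 48 = 10.4%.
4. Chance background for a count, taking +30 ms purely as an example step and changes centred on zero: expected number = 48 × P(change > 30).
   - SD 10: 48 × 0.0013 = 0.06. SD 14: 48 × 0.016 = 0.77.
   - Fewer than one chance exceedance is expected per treatment, against 2 or 5 affected subjects.
5. What the planned SD would show = √(SD² + p(1 − p)d²), where p is the share affected and d the increase.
   - 2 of 48 at +60 ms: p(1 − p)d² = (2/48)(46/48)(3600) = 143.75. The SD goes from 10 to √243.75 = 15.6 ms, or from 14 to √339.75 = 18.4 ms.
   - The SD would therefore signal that something is present, but not in how many subjects.
6. Limit of a count: zero affected subjects gives a one-sided 95% upper bound of 1 − 0.05^(1/n), which is 5.8% at n = 50 and 7.2% at n = 40.

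**The case against.** The strongest case for the plan has four parts.

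- **It delivers what the protocol asks.** Protocol 4.2.1 calls for observed values and changes, and Protocol 10.5 for changes from baseline summarised by treatment group and timepoint. SAP 15.5 does this and adds a shift table. This stands: the gap is an omission, not a contradiction.
- **An extreme value would not be hidden.** The SD and the maximum would stand out beside the placebo column, and with about 50 subjects a reader could count and pair cases from the listing. This stands as far as detection goes. It leaves the count to be made by hand, with a limit chosen after seeing the data.
- **The documents offer no on-treatment threshold.** No step such as 30 or 60 ms appears anywhere, and 440 ms is an entry limit at screening. A subject just below it at screening could exceed it at a period baseline with no drug effect, and the 375 to 435 ms example would not be caught by it. This stands too. It is why the value category must be set against the period-baseline category, and why increases need their own categories.
- **The Appendix C table index is not shown.** An unlisted QTcF table cannot be excluded; the text of 15.5 specifies none.

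A reader might also go further and infer that the shift table compares baseline with the off-drug visit, because SAP 4 says each subject "will undergo a follow-up assessment approximately 1 to 2 weeks after the last dose of trial treatment". The documents do not support that. SAP 15.5 and the visit table in SAP 9 call that visit End of Trial, 15.5 summarises it overall rather than by treatment, and the shift table is split by treatment with percentages for each visit. The more natural reading includes Day 14. What remains is an undefined word. SAP 15.3 confines the by-treatment vital-sign summaries to time points in the treatment periods; 15.5 has no such limit.

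**Conclusion.** The readable text of SAP 15.5 specifies no categorical QTcF summary by treatment, and the one categorical ECG table need not respond to a QTcF rise. As planned, the report would show whether an extreme value occurred. It would not tabulate how many subjects were affected on each treatment, or whether the same subjects were affected on both.

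On the assumptions above, two subjects at +60 ms would move the mean by 2.4 to 3.0 ms for n from 50 down to 40, while a count would show them directly. The claim is not that the mean can never show such a pattern: five subjects at +40 ms would just exceed the half-width at the smaller assumed SD. The textual finding does not depend on these assumptions.

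This is a worthwhile addition to a primary safety analysis, not an error that invalidates it. The *follow-up* wording is a minor point, and the conclusion does not depend on it: even a Day 14 shift in overall interpretation would not count QTcF prolongation.

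**What to change.** Add one table to SAP 15.5: subject counts and percentages by treatment at Day 14 of each period, with early-withdrawal ECGs assigned as in SAP 8.3, showing

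- QTcF value category, for example with the protocol's 440 ms entry limit as a descriptive reference, set against the category at period baseline;
- increase from period baseline, in steps that the sponsor fixes before unblinding;
- for both, a within-subject cross-tabulation of ADX-629 against placebo.

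State that these are descriptive categories and not clinical action limits. In the shift table, replace *follow-up* with the named visit, Day 14 of the same treatment period.

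The cost is some SAP wording and one table from ECGs already collected, with no change to any procedure. The downside is a few chance exceedances on both treatments, which the placebo column and the cross-tabulation help the reader to judge. If the blind has already been broken, SAP 8 requires the table to be labelled post hoc.
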